## 1. BACKGROUND INFORMATION

A full description of the indication, investigational medicinal product (IMP), preclinical and clinical data available for GT005 is provided in the Investigator's Brochure (IB).

## 1.1 Indication

Age-related Macular Degeneration (AMD) is the most common cause of blindness among the elderly in the industrialised world [Jonasson 2014], affecting approximately 36 to 40 million people globally [Access Economics Report 2010]. AMD is a progressive disease that results in a blurred area or blank spot in the centre of vision [NIH].

AMD is classified into early, intermediate, and late stages [Ferris 2013]. Late-stage AMD includes two morphological sub-types: choroidal neovascular AMD (CNV) and Geographic Atrophy (GA) [Chakravarthy 2010]. There are no approved therapies for GA.

## 1.2 Investigational Product

GT005 is a recombinant adeno-associated viral (AAV) vector derived from wild-type AAV serotype 2 (AAV2). █

The vector genome is designed to enable cellular transduction and induce secretion of CFI via a unique subretinal delivery. GT005 is stored at <-60°C.

### 1.3 Findings from Preclinical Studies

A detailed description of the preclinical data is provided in the IB.

## 1.4 Clinical Studies

A single first-in-human study evaluating the safety, dose response and efficacy of three doses of GT005 administered by subretinal injection to subjects presenting with GA due to AMD is ongoing.

## 1.5 Study Rationale

### ***1.5.1 The Complement Cascade***

Evidence has emerged which implicates chronic local inflammation and activation of the complement cascade in AMD pathogenesis [Anderson 2010]. A number of complement proteins have been identified as constituents of drusen, the hallmark extracellular deposits associated with AMD [Anderson 2010]. Variants in genes of complement factors involved in the alternative pathway (Complement Factor H, CFI, Complement Factor B, and Complement component 3 [C3]) have been found in AMD patients [Fritzsche 2016]. The results of a number of genome-wide association studies suggest that mutations in these genes strongly correlate with the likelihood of developing AMD [Fritzsche 2013; Fritzsche 2016]. Additional studies have found that some rare genetic variants of CFI (defined by a minor allele frequency <1%) are associated with increased risk of advanced AMD, with one study showing that low serum CFI levels together with the presence of rare CFI variants is associated with an increased risk of development of advanced AMD [Seddon 2013; Kavanagh 2015; Geerlings 2017].

### **1.5.2 Rare Variant Genetic Population (Part 1)**

As CFI serves as a global down-regulator of the alternative pathway [Lachmann 2016], an increase in intraocular CFI level has the potential to dampen an over-activated complement system, reducing the progression of the disease. The subset of GA patients with CFI rare variant genotype associated with a low serum CFI may demonstrate a larger response to treatment that supplements CFI locally, correcting the effects of their complement gene mutation. AAV2 vector-based CFI gene transfer (GT005) provides a sustained expression of human CFI in AMD

patients' eyes and is expected to result in down-regulation of the alternative complement pathway.

Part 1 will only consider CFI rare variant genotypes previously associated with low serum CFI or subjects carrying an unreported CFI rare variant genotype that have tested to have a low serum CFI for study entry.

Part 1 of the study will close for enrolment once all appropriate approvals for protocol V6.0 are in place; subsequently, subjects with GA and a CFI rare variant genotype should then be entered into Part 2 of the study.

#### ***1.5.3 Broad Genetic Population (Part 2)***

Part 2 of the EXPLORE Phase II clinical study aims to assess the safety and efficacy of GT005 in a broad population of GA subjects, regardless of genotype.

Overactivation of the complement system is also implicated in the risk of disease development across the broader dry AMD population, as shown by significant enrichment of common genetic risk factors mapping to complement proteins involved in the alternative pathway e.g. complement factor H (CFH), CFI, complement factor B (CFB), and complement component 3 (C3) [Fritsche 2013; Fritsche 2016]. Rare, functionally damaging variants in CFH, CFB and C3 strongly predispose to AMD [Raychaudhuri 2011; Seddon 2013; Zhan 2013; Saksens 2016]. Other more common AMD risk variants mapping to CFH and CFI are also implicated in AMD, however their contribution to disease development is much weaker, given their overall high prevalence across healthy individuals who never develop AMD [Fritsche 2016]. However, in combination, these weak risk variants may exert a larger (additive) effect on the delicate balance between complement activation and regulation [Harris 2012].

Part 2 is designed to evaluate whether administering CFI will be effective in down-regulating a hyperactive complement system across all GA patients from a broad genetic population and if this intervention will have a therapeutic effect on disease progression. This hypothesis is postulated from the observation that CFI supplementation has the potential to normalise variation in complement activity in blood sera taken from individuals carrying different combinations of common complement risk variants [Lachman 2016].

#### ***1.5.4 Dose Rationale***

It has been shown that a 22 µg/mL increase in systemic CFI concentration can reduce the activity of the C3b feedback cycle of the highest risk sera to that of the lowest risk [Lachmann 2016]. It has been demonstrated that normal levels of CFI in plasma and vitreous humor are

28,366 and 691 ng/mL, respectively [Mandava 2019].

## 1.6 Risk/Benefit Assessment

A summary of data and guidance to the Investigator is provided in the IB.

### 1.6.1 Potential Risks

The risks associated with this study can be divided into those related to the GT005 product, the surgical delivery of GT005, and study procedures.

### 1.6.1.1 Risks Associated with GT005

There were no GT005-related systemic adverse effects with all doses tested in both the monkey and mouse toxicity studies. In mice, [REDACTED]

The potential risks associated with gene therapy are related to intraocular inflammation, immunogenicity, developmental risks, germ line transmission, and environmental risks as discussed below.

[REDACTED]

An immune response to human CFI is the most likely cause for the observed inflammatory changes in both studies. This is based upon detection of anti-CFI antibodies which correlated with incidence and severity of the findings in the retina and geniculate nucleus in monkeys. Since the generation of antibodies to human CFI is not expected in subjects, these adverse findings are likely species-specific.

[REDACTED]

**Immunogenicity** of the recombinant AAV platform has been extensively assessed in over 200 clinical studies to date [Ginn 2018], several of which were ocular gene therapy studies using subretinal injection of AAV2 vector. There have been no reported ocular toxicities observed which have been attributed to an immune response to the capsid in the treated subjects. When administered subretinally, the humoral and cellular immune response to the capsid has been limited compared to systemically administered recombinant AAVs. After repeat administration of voretigene neparvovec, there was little to no change reported in antibody titres to AAV capsid when measured in systemic circulation and seemingly no correlation between presence of anti-capsid antibodies and clinical safety or efficacy [Voretigene Neparvovec FDA ACM 2017; Migozzi 2013].

[REDACTED]

[REDACTED]

[REDACTED]

[REDACTED]

[REDACTED]

[REDACTED]

[REDACTED]

[REDACTED]

[figure not shown]
[REDACTED]

**Raised CFI levels** are expected locally in the retina without impacting the systemic complement system. While inhibition of the complement system has been associated with an increased risk of microbial infection, supplementing CFI locally does not block complement activation but merely normalises complement regulation. As such, increased susceptibility to infection would not be predicted. CFI is a normal plasma protein and acute phase protein plasma levels may rise by 150% at times of inflammation [Gleeson 2016]. Following the local injection of GT005, it is unlikely that serum levels will exceed the ranges seen in healthy individuals in various physiological states.

**Reproductive and developmental abnormalities** have not been reported following subretinal or systemic AAV-based gene therapy [Provost 2005].

[REDACTED]

[REDACTED]

**Environmental risks** are considered to be low, because the GT005 AAV vector is replication-deficient and has been stripped of all genetic machinery that would enable infective virions to develop. GT005 is considered to pose negligible risk to humans, animals, and the environment.

#### **Retinal Pigment Epithelium (RPE) Changes**

Pigmentary changes have been noted in the RPE of some subjects receiving GT005 via subretinal delivery (Refer to the IB for further information). These changes are limited to the bleb area and in most cases were first seen at Week 12 and are identifiable on FAF. In a minority of cases an area of depigmentation can also be seen on colour fundus photography (CFP).

#### **1.6.1.2 Risks Associated with the Surgical Procedure and Study Procedures**

The surgical technique employed for this clinical study has been developed for and successfully used for the choroideremia subretinal gene therapy clinical studies [MacLaren 2014; Xue 2017]. Risk mitigation strategies have also been developed to minimise foveal or retinal stretch during vector delivery, or prevent post-surgical ocular inflammation. A careful pre-operative assessment of the retina is done as part of surgical planning, with a range of visual function tests as well as retinal imaging to determine the functional and structural integrity of the targeted retina. The risks include:

**Intraocular inflammation** [REDACTED] A transient visual loss may be observed in the first days post-surgery due to the bleb related foveal detachment. This can be minimised by avoiding injecting into areas of retinal thinning and by not detaching the fovea, if it is deemed not necessary. Retinal detachment usually regresses over 24 hours when the subretinal fluid resolves and retinotomy self-seals. Structural recovery of the retina following iatrogenic detachment of the macula generally occurs within 1 month [Xue 2017]. Persistent retinal detachment, due to persistence of the vector bleb, can occur in less than 1 in 100 cases and may be effectively managed by retinopexy with or without appropriate intraocular tamponade. An ocular examination of the eye treated with GT005 will be performed by the Vitreoretinal Surgeon or designee on post-surgical Day 2, at Week 1 (Day 8) and Weeks 5, 12, 24, 36, 48, 72, and 96 to ensure adequate monitoring. Subjects will also be contacted by telephone per the schedule of assessments for the review of adverse events (AEs).

**Cataract formation** is associated with any vitrectomy procedure and is also a risk of periocular or topical steroid use. In a published study from [Feng 2014], cataract appeared in approximately 40% of subjects following pars plana vitrectomy and resulted in a cataract extraction over the following 2 years. In publicly available safety data, voretigene neparvovec

(Luxturna®), a subretinally delivered AAV2-RPE65 for the treatment of RPE65 retinal dystrophy, was administered in 81 eyes and of those, 11 eyes (14%) from seven subjects had documented progression of existing cataract or formation of new cataract. Three subjects had their cataract successfully extracted and other cataract cases did not receive elective extraction procedures [[Voretigene Neparvovec FDA ACM 2017](#)]. The study population of advanced AMD subjects is expected to have a mean age above or equal to 60 years and therefore may have already undergone a cataract extraction. At screening, subjects participating in this GT005 study and assessed as likely to require cataract surgery during the 12-month study period will not be included or will be offered the option of removing their cataract before being (re)screened in the study. Participants who develop cataracts during the study may undergo cataract surgery if deemed clinically necessary; if surgery is performed, it should be carried out at least 4 weeks before Week 48 visit.

**Intraocular pressure elevation** is a risk associated with vitrectomy procedures [[Chang 2006](#)] and periocular or topical steroids [[Kersey 2006](#)]. In publicly available safety data, voretigene neparvovec (Luxturna®), had reports of elevation in intraocular pressure in 8 of 81 eyes treated (10%). Subjects will have intraocular pressure (IOP) checked at every visit to ensure adequate monitoring and therapies prescribed as needed based on local standard. At screening, subjects with moderate or advanced glaucoma will not be included in the study to minimise this risk.

**Worsening of vision** is an uncommon risk associated with the surgical procedure or vitreous tap and could be the result of endophthalmitis or retinal damage. Risk is mitigated by design of the surgical procedure, Surgeon qualification standards, and close monitoring post-operatively.

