## PROTOCOL SYNOPSIS

SPONSOR: Gyroscope Therapeutics
INVESTIGATIONAL MEDICINAL PRODUCT: GT005: A recombinant adeno-associated viral vector derived from wild-type adeno-associated virus serotype 2 (AAV2). The expression cassette contains deoxyribonucleic acid encoding for human Complement Factor I (CFI).
TITLE: EXPLORE: A Phase 2, outcomes assessor-masked, multicentre, randomised study to evaluate the safety and efficacy of two doses of GT005 administered as a single subretinal injection in subjects with geographic atrophy secondary to age-related macular degeneration.
PROTOCOL NO: GT005-02 (EXPLORE)
INDICATION: GT005 is under development for the treatment of geographic atrophy (GA) secondary to age-related macular degeneration (AMD).
INVESTIGATOR STUDY SITES: Approximately 60 study sites will take part. Designated sites will perform screening and subretinal surgery for subjects allocated to GT005, and post-operative follow-up visits.
STUDY PERIOD: Subject participation consists of a screening period of up to 8 weeks and a 96-week study period, for a total of 104 weeks.
STUDY RATIONALE: Age-related macular degeneration is the most common cause of blindness among the elderly in the industrialised world [Jonasson 2014], affecting approximately 36 to 40 million people globally [Access Economics Report 2010]. AMD is a progressive disease that results in a blurred area or blank spot in the centre of vision [NIH]. AMD is classified into early, intermediate, and late stages [Ferris 2013]. Late-stage AMD includes two morphological sub-types: choroidal neovascular AMD (CNV) and GA [Chakravarthy 2010]. At the time of writing, there are no approved therapies for GA. Evidence has emerged which implicates chronic local inflammation and activation of the complement cascade in AMD pathogenesis [Anderson 2010]. A number of complement proteins have been identified as constituents of drusen, the hallmark extracellular deposits associated with AMD [Anderson 2010]. Variants in genes of complement factors involved in the alternative pathway (Complement Factor H, Complement Factor I (CFI), Complement Factor B, and Complement component 3) have been found in AMD patients [Fritsche 2016]. These results suggest that mutations in these genes strongly correlate with the likelihood of developing AMD [Fritsche 2013; Fritsche 2016].

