### 4.2 Exclusion Criteria

Subjects will NOT be included in the study if they meet any of the following criteria:

- 1) Subjects who have a clinical diagnosis of Stargardt Disease or other retinal dystrophies, confirmed by the central reading centre
- 2) Have a history, or evidence, of CNV in the study eye
- 3) Presence of moderate/severe or worse non-proliferative diabetic retinopathy in the study eye
- 4) Have history of vitrectomy, sub-macular surgery, or macular photocoagulation in the study eye
- 5) History of intraocular surgery in the study eye within 12 weeks prior to Screening (Visit 1). Yttrium aluminium garnet capsulotomy is permitted if performed  $>10$  weeks prior to Visit 1

- 6) Have clinically significant cataract that may require surgery during the study period in the study eye
- 7) Presence of moderate to severe glaucomatous optic neuropathy in the study eye; uncontrolled IOP despite the use of two or more topical agents; a history of glaucoma-filtering or valve surgery is also excluded
- 8) Axial myopia of greater than -8 dioptres in the study eye
- 9) Have any other significant ocular or non-ocular medical or psychiatric condition which, in the opinion of the Investigator, may either put the subject at risk or may influence the results of the study
- 10) Have a contraindication to specified protocol corticosteroid regimen
- 11) Have received any investigational and/or approved product(s) for the treatment of GA within the past 6 months, or 5 half-lives (whichever is longer) other than nutritional supplements such as the age-related eye disease study (AREDS) formula in the study eye or systemically
- 12) Have received a gene or cell therapy at any time
- 13) Are unwilling to use two forms of contraception (one of which being a barrier method) for 90 days post-dosing, if relevant
- 14) Active malignancy within the past 12 months, except for: appropriately treated carcinoma in situ of the cervix, non-melanoma skin carcinoma, or prostate cancer with a stable prostate-specific antigen (PSA)  $\geq 12$  months

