#### 6.1.13 Visit 10, Week 72 (Local or Surgical Site)

The following assessments will be performed for ALL subjects unless otherwise specified:

- Concomitant medication
- Vital signs
- Biochemistry/haematology
- AEs
- Ophthalmic examination

- CFP
- FAF
- OCT macula
- [REDACTED]
- [REDACTED]
- BCVA using ETDRS
- LLVA using ETDRS for LLD
- MNRead
- VFQ-25
- FRI Index
- OCT-A and/or FA if clinically indicated (if a subject converts to wet AMD)
- [REDACTED]
- [REDACTED]

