### 7.3.1 Ophthalmic Examination

Ophthalmological examinations in both eyes will be performed as follows: anterior segment examination via slit lamp biomicroscopy, intraocular pressure via Goldmann applanation tonometry (GAT) or a Tono-Pen®, posterior segment and fundus examination via dilated indirect ophthalmoscopy. Ocular inflammation will be assessed.

Slit lamp will be conducted on both eyes. The eyelids, cornea, conjunctiva, anterior chamber, iris/pupil and lens should be evaluated. Findings will be graded as normal, abnormal non-clinically significant, or abnormal clinically significant. Cataract will be graded using the AREDS clinical lens grading system [Appendix 17.1]. Intraocular pressure should be assessed using the same method (GAT or Tono-Pen®) throughout the study, regardless of method chosen.

Dilated indirect ophthalmoscopy will assess the vitreous, macula, choroid, optic nerve, retina and cup- to-disc ratio of both eyes. Findings will be graded as normal, abnormal non-clinically significant, or abnormal clinically significant.

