### 8.3 Adverse Events of Special Interest

An AESI (serious or non-serious) is one of scientific and medical concern specific to the Sponsor's product or program, for which ongoing monitoring and rapid communication by the Investigator to the Sponsor can be appropriate. AESIs should also be assessed as to whether it fits the criteria of an SAE and reported appropriately.

It is anticipated that there may be transient decreases to visual acuity related to the subretinal injection surgical procedure. A transient visual loss may be observed in the first days post-surgery due to bleb-related foveal detachment, if performed. Transient surgery-related events of decreases in visual acuity are defined as decreases occurring in close temporal association (within 24 hours) with the surgical administration of the study medication, and which are resolving at Week 1 (Visit 3) post-surgery.

Additionally, there is a known risk of cataract associated with any vitrectomy procedure. A published review from [Feng 2014] shows cataract to be common following pars plana vitrectomy with about 40% of patients requiring a cataract extraction over the following 2 years.

Transient, surgically-related decreases in visual acuity, as well as cataract will not be classified as AESI.

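### The readable SAP leaves out, without declaring it, the cataract-grade and intraocular-pressure summaries specified in the protocol; separately, the protocol's cataract-surgery paragraph was not updated for 96-week follow-up

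*Protocol*

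**What the plan says.** **Lens and pressure data.** Protocol 7.3.1 requires an ophthalmic examination of both eyes, including IOP. On the lens it says: "Cataract will be graded using the AREDS clinical lens grading system". The examination is scheduled for both arms at screening and at Weeks 12, 24, 36, 48, 72 and 96 (Tables 1 and 2). The Week 72 list, for example, opens: "The following assessments will be performed for ALL subjects unless otherwise specified". Protocol 9.4.3, and the safety paragraph of the synopsis, commit to summarising these examination findings and name cataract grade and IOP.

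**Expected risk.** Protocol 8.3 cites a published review of pars plana vitrectomy, with "about 40% of patients requiring a cataract extraction over the following 2 years". The same section keeps cataract out of the adverse events of special interest.

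**SAP.** Section 2.7 covers adverse events, deaths, loss of best corrected visual acuity (BCVA), laboratory data and other safety data. The last of these, 2.7.5, holds only ECG (not applicable) and vital signs. Section 4 lists the changes from the protocol.

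**Cataract surgery on study.** Protocol 1.6.1.2 says that subjects "assessed as likely to require cataract surgery during the 12-month study period will not be included", or may have the cataract removed before screening again. For cataract that develops later, surgery is allowed when clinically necessary, and "if surgery is performed, it should be carried out at least 4 weeks before Week 48 visit". The synopsis gives participation as "a screening period of up to 8 weeks and a 96-week study period, for a total of 104 weeks".

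**The concern.** The control arm has no surgery, so any cataract or pressure effect of the procedure falls on the GT005 arms alone. Lens opacity lowers BCVA. BCVA is both an efficacy and a safety measure here, and SAP 2.7.3 counts losses of 15 and 30 letters up to Week 96. A reader who sees more letter loss on GT005 would want to know how the lenses changed. The protocol planned a direct readout of that; under the SAP as written it would not be produced.

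The timing paragraph is a smaller matter. Its apparent purpose is to keep recent cataract surgery away from an endpoint visit. With BCVA followed to Week 96, the advice covers the primary visit but neither second-year visit.

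**Working it through.** **1. Promise against plan**

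| Item | Protocol | Readable SAP |
|---|---|---|
| Cataract grade | To be summarised (9.4.3, synopsis) | No output in 2.7.1-2.7.5 |
| IOP | To be summarised (9.4.3, synopsis) | No output in 2.7.1-2.7.5 |
| BCVA | To be summarised (9.4.3, synopsis) | Model (2.6.2) and letter loss (2.7.3) |
| Cataract as an adverse event | To be summarised (9.4.3) | By arm and eye (2.7.1) |
| Cataract extraction | Not named in 9.4.3 | Concurrent procedures by arm and eye (2.4.2) |
| Baseline lens status | Not named (9.4.1) | Not among the 17 ocular items (2.3.2) |

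SAP section 4 declares four things: removal of the Week 48 interim analysis, removal of the safety set, a simplified estimand with a mixed model for the primary endpoint, and no subgroups. The ophthalmic examination is not mentioned. The SAP's caveat that outputs depend on data availability after termination appears in 2.5.2 and 2.6.2 (efficacy), not in 2.7.

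One limit applies. Two SAP contents entries between 2.10 and section 3 cannot be read, so absence is stated for the readable text only. Section 2.7 is numbered without a break, and section 4 is readable.

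**2. The cataract paragraph against the rest of the protocol**

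- Cataract paragraph: a 12-month study, about 52 weeks, with one timing reference at Week 48 - 4 = Week 44.
- Same section, inflammation paragraph: examinations at "Weeks 5, 12, 24, 36, 48, 72, and 96 to ensure adequate monitoring".
- Exclusion 6 (Protocol 4.2): "Have clinically significant cataract that may require surgery during the study period in the study eye". This follows the current duration.

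Only the cataract paragraph was left behind. The Amendment History shows that participation was extended from 48 to 96 weeks in V4.0.

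**3. How many eyes would the new timing advice touch?**

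Inputs from the protocol: 202 subjects, 2:1 allocation, and a 40% extraction rate over 2 years (104 weeks). Assumptions: extractions are spread evenly over the 2 years; 30% to 100% of GT005 eyes are at risk (100% if the cited rate already refers to all subjects); enrolment and follow-up are complete.

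- GT005 eyes: 202 × 2/3 = 134.7
- Extractions over 2 years: 0.40 × 0.30 × 134.7 = 16.2, up to 0.40 × 1.00 × 134.7 = 53.9
- Added windows: 4 weeks before Week 72 plus 4 weeks before Week 96 = 8 weeks, and 8/104 = 0.077
- Eyes in those windows: 16.2 × 8/104 = 1.2, up to 53.9 × 8/104 = 4.1
- As a share of GT005 eyes: 1.2/134.7 = 0.9%, up to 4.1/134.7 = 3.1%

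**The case against.** **Cataract is not lost from the report.** Events and extractions are tabulated by arm and eye, and BCVA and medical history are listed. Abnormal investigation findings can count as adverse events (Protocol 8.1), and investigators must check other collected data for them (7.4.2). This stands, and it narrows the gap to graded change that nobody reported as an event or operated on. IOP is in the same position.

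**The SAP was cut back generally after termination.** By-visit laboratory tables are dropped and vital signs reduced to a listing. That probably explains the omission. But the laboratory cut is stated where it is made, and section 4 exists to record departures; the ophthalmic examination appears in neither place.

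**Baseline lens status was never promised.** This is correct, so its absence is not a departure from the protocol.

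**Protecting only Week 48 is defensible.** It is the primary visit, the text sits in a risk section, and exclusion 6 governs eligibility correctly. This stands as a reason to call the point minor. It does not supply advice for the second-year visits.

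**A stronger reading of the timing sentence.** A reader might infer that surgery is forbidden after Week 44. The documents do not support that. The sentence first allows surgery for cataract arising during the study whenever clinically necessary, with no time limit, and the timing clause is advisory. Once Week 48 has passed, spacing before it has no force.

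**Conclusion.** The point holds and is minor. Followed as written, the readable SAP omits a safety output that the protocol specifies, for a risk expected only in the operated arms, and does not say so. Separately, the cataract paragraph of Protocol 1.6.1.2 does not fit 96-week follow-up.

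Three inferences would go too far. Cataract as such does not go unreported, because the event and procedure tables remain. No eligibility error follows, because exclusion 6 is worded correctly. No bias in BCVA is shown: the documents give neither the share of eyes with a natural lens nor the letter loss per grade, so no size is claimed.

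The only figure is the reach of the proposed timing advice, roughly 1 to 4 GT005 eyes. It rests on the 30-100% at-risk range, an even spread of extractions and full follow-up; early termination would lower it. BCVA is a secondary endpoint, Protocol 9.4.2 plans no inferential testing, and termination thins the late data.

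**What to change.** **SAP 2.7.5.** Restore by-visit summaries, by arm and eye, of AREDS cataract grade (nuclear, cortical and posterior subcapsular) and of IOP. Both are already collected, so the cost is programming the tables; the Week 72 and 96 rows will be sparse. No additional BCVA model is requested. By-arm tables will not link lens change to letter loss within a subject, but they will show whether the arms differ in lens change. Noting the removal in section 4 would repair the record but would not supply the output.

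**SAP 2.3.2 (optional).** Add one row for study-eye lens status at baseline (phakic or pseudophakic), taken from ocular surgical history.

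**Protocol 1.6.1.2, cataract paragraph.** Change the 12-month period to 96 weeks, and replace the timing sentence with: *Cataract surgery may be done at any time if clinically necessary; when it can be deferred, it should avoid the 4 weeks before the Week 48, 72 or 96 visit.* The cost is two sentences and a delay of up to about 4 weeks for the few eyes estimated above. It cannot alter the eligibility of subjects already enrolled, and with the programme stopped it serves mainly to make the document accurate.
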